Glucose meter and insulin rate reporting: The research assistant will provide instructions for the participant to report readings from their diabetes devices. For continuous glucose sensor and insulin pump users, device data for the past month will be provided through data exports from the device software for sharing with healthcare teams, with no medical device ID or personal identifiers retained. For glucose meter users, they will report glucose readings for the last 7 days from their glucose meter. For insulin injection users, they will report long-acting insulin doses and carbohydrate exchange ratios used over the last 7 days.

As the final activity of the baseline assessment, the participants will be randomized to the Activate program or treatment-as-usual and receive instruction, if required on completing the intervention program, and for all the follow-up assessment.

After twelve weeks, adolescents and their primary caregiver will repeat the entire baseline assessment battery in a second video-based lab appointment. Adolescents will receive \$25 for the intake assessment and \$50 for the follow-up assessment on a study provided cash card or gift card. Adolescents will return the assessment toolkit with a pre-paid mailing label.

Intervention: Activate Program

Adolescents randomized to the active condition will participate in a 12-week online diabetes behavior-change skills training and physical activity promotion program. See attached intervention guide for protocols beyond description below.

Diabetes Behavior-Change Skills Training. Behavior-change skills training will be provided through eight web-delivered content and activity sessions across the 12-week program. Sessions 1 through 4 will occur weekly and sessions 5 through 8 biweekly. Each session takes approximately 15-20 minutes for the adolescent to complete both content learning and related activities. Session 1 (week 1 of program) provides an introduction to the entire Activate Program as well as a goal-setting activity related to type 1 diabetes management. Sessions 2-8 (weeks 2 to 12 of the program) provide physical activity reminders that overlap with text-based support for the physical activity program (see below) as well as specific session content for behavior-change skills training: goal setting, goal planning and rewards, identifying challenges, problem-solving, increasing social support and positive activities, and managing strong emotions.

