Physical Activity Incentives Program. The physical activity incentives program includes 12 weeks of personalized goals and incentives for increasing physically active minutes along with weekday text-based support. Active minutes, defined as minutes with moderate to vigorous physical activity, will be tracked via a Garmin fitness activity tracker, which is synced to a coded study-specific account via PhysioQ's Labfront, a secure site used to collect and manage Garmin fitness activity tracker data. All data will be deidentified and only accessible to the research team. In week 1, all adolescents will receive incentives for syncing their Garmin fitness activity tracker on at least five days. In weeks 2 to 12, adolescents will receive personalized daily and weekly activity goals based on their progress. Daily incentives will be offered for meeting daily goals, and increased earnings will be available for meeting weekly bonus goals. Maximum earnings across the 12 weeks will be \$430. Weekdays, text-based support will be provided to remind adolescents of goals and earning potential as well as additional support to problem-solve technology and physical activity difficulties when indicated. Education prior to the intervention will follow American Diabetes Association³¹ guidance including information about how insulin requirements change with increased physical activity and how to prevent hypo and

hyperglycemia during and after exercise as well as reviewing the adolescent's plans for managing low blood glucose and contacting their pediatric endocrinologist with questions about glucose management with increased physical activity. All incentives will be delivered weekly on a cash card provided by the study or via gift card(s) provided at an interval chosen by the participant.

Treatment-as-Usual Control condition. For those in treatment as usual, participants will be trained to wear a Garmin fitness activity tracker daily for the next 12 weeks and asked to follow their standard care for diabetes management.

Describe required screening procedures performed before enrollment and while on study.

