Data and Safety Monitoring Plan –As noted above, risks associated with this study are minimal and are not believed to exceed those adolescents already encounter in daily life. Specifically, the behavior change skills training and physical activity program is designed to help participants come closer to meeting the widely accepted guideline of engagement in at least one hour of moderate intensity physical activity each day (AHA and CDC^{61,62}). This level of involvement is believed necessary to yield optimal health benefits in persons with diabetes (ADA⁶⁴). Consequently, given the minimal risk nature of the protocol, the primary monitor of the data and participant safety will be Drs. [name]; this monitoring will occur on an ongoing basis, with the status of participant adolescents discussed at weekly meetings. Any adolescent experiencing difficulty with the physical activity program will be referred via the adolescent's parents to their physician for evaluation. The research team will document and review any adverse events that occur for each participant during the study. At baseline and 12-week follow up appointments, a research assistant will complete an adverse event form with the participant where they will be asked about any adverse events they have experienced over the past 3 months, in order to compare adverse events pre and post study, and between study conditions. Participants randomized to the intervention program will also have access to the adverse events form throughout the study period for additional reporting should they require it. We will also have an independent medical monitor review our summary of adverse event reports. Any adverse event will be reported to the local Institutional Review Board (IRB) in accordance with local guidelines. In addition, [name] will be responsible for assembling the study data and assisting in the preparation of annual data and safety monitoring reports. She will ensure that all monitoring plan personnel obtain copies of these reports in a timely fashion, prior to the deadline for each review. [name] will also oversee all communications with the Office of Research Protections to specifically include initial study approval; ongoing continuation reviews; and any necessary reporting of protocol deviations, protocol modifications, personnel changes, or adverse events.

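### The follow-up adverse event look-back runs from the visit rather than from randomisation, so it matches time on study only when the visit falls at about 13 weeks

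*Protocol*

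**What the plan says.** The Data and Safety Monitoring Plan in the Protocol sets the adverse event schedule: "At baseline and 12-week follow up appointments, a research assistant will complete an adverse event form with the participant". On that form "they will be asked about any adverse events they have experienced over the past 3 months", and the stated purpose is "in order to compare adverse events pre and post study, and between study conditions". The same look-back therefore applies at both appointments and is counted back from each appointment.

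The Procedures section fixes the two ends of the study period. Randomisation closes the first appointment: "As the final activity of the baseline assessment, the participants will be randomized to the Activate program or treatment-as-usual". The second appointment follows: "After twelve weeks, adolescents and their primary caregiver will repeat the entire baseline assessment battery in a second video-based lab appointment". Neither an earliest nor a latest permitted date is given for it.

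The Physical Activity Incentives Program section says when the activity demand begins. Week 1 rewards only syncing of the tracker; after that, "In weeks 2 to 12, adolescents will receive personalized daily and weekly activity goals based on their progress".

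The monitoring plan has two further provisions. The team is to record and examine adverse events arising in any participant during the study. In addition, "Participants randomized to the intervention program will also have access to the adverse events form throughout the study period". No equivalent access is stated for the control arm. The Statistical Analysis Plan does not mention adverse events.

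**The concern.** An on-study adverse event count should cover the time from randomisation to the follow-up visit, no more and no less. A window of 3 months counted back from the visit does this only if the visit happens to fall 3 months after randomisation, and the planned interval is 12 weeks, which is shorter.

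Two consequences follow. If the visit is punctual, the window reaches into days before randomisation that the baseline form has already covered, so a single event could be entered as both pre and post. If the visit is late enough, the window opens after randomisation and the first days on study fall outside the scheduled form. The Risks section names overexertion and glucose changes with increased activity as the program's physical risks, so the start of the activity goals is a period that the safety comparison should cover.

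**Working it through.** The plan gives no figure of its own to reproduce. The check is calendar arithmetic.

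**Inputs**
- Look-back L: 3 calendar months (Data and Safety Monitoring Plan). Over every possible visit date in a four-year cycle this is 89 to 92 days, mean 91.3.
- Randomisation: day 0, at the end of the baseline appointment (Procedures).
- Planned follow-up: T = 12 × 7 = 84 days (Procedures).
- Later visits: assumed values of T, because no visit window is stated.
- Activity goals: from program week 2 (Physical Activity Incentives Program). I assume week 1 starts at randomisation, so goals start on day 8.

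**Formulas**
- Pre-randomisation days in the window = max(0, L − T)
- Early study days not covered = max(0, T − L)

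| Follow-up visit | T (days) | Pre-randomisation days included | Early study days not covered |
|---|---|---|---|
| 12 weeks | 84 | 5–8 (mean 7.3) | 0 |
| 13 weeks | 91 | 0–1 | 0–2 |
| 14 weeks | 98 | 0 | 6–9 |
| 15 weeks | 105 | 0 | 13–16 |
| 16 weeks | 112 | 0 | 20–23 |

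**On-time visit.** 89 − 84 = 5 and 92 − 84 = 8. As a share of the window, 7.3 / 91.3 = 8.0% (range 5/89 = 5.6% to 8/92 = 8.7%).

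**Late visits and the goal period.** Goal days missed = max(0, days not covered − 7).
- 14 weeks: 0 to 2 goal days. The loss is all or nearly all in week 1.
- 16 weeks: 20 − 7 = 13 to 23 − 7 = 16 goal days, so all of weeks 2 and 3, or all but one day, and at most two days of week 4.
- The first goal day is lost only once T exceeds L + 7, that is 96 to 99 days, or 12 to 15 days after the planned date.

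**With the follow-up question anchored to baseline.** The window equals T whatever the visit date, so pre-randomisation days are 0 and uncovered days are 0. The two windows then differ in length. Under a constant event rate, the raw post/pre count ratio would be 84 / 91.3 = 0.92 at 12 weeks and 112 / 91.3 = 1.23 at 16 weeks. Dividing by person-weeks removes that artefact.

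**The case against.** The strongest reply is that equal 3-month windows are deliberate. They make the pre/post comparison like-for-like, and the mismatch at 12 weeks is about a week, which is finer than an adolescent's recall of 3 months. A visit a week after the planned date gives an almost exact match. The trial has 60 participants, is described as minimal risk, and has no planned adverse event model, so no primary or secondary result changes. All of this stands and limits the weight of the point. But windows of equal length do not give a clean pre/post contrast if they overlap.

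A reader might also infer more than the documents support:

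- *That any late visit loses the first weeks of activity goals.* It does not. The first 5 to 8 days of delay only remove the overlap, and about the next week of delay drops only week 1. The documents give no evidence of how late visits will be.
- *That early Activate events would be lost.* The scheduled form may miss them, but the team is to document events throughout, and Activate participants can use the form between visits and have weekday text contact. That form access is optional, so capture is likely but not assured. The less protected arm is control.
- *That the overlap biases the arm comparison.* It precedes randomisation and is expected equally in both arms, so it dilutes the comparison rather than tilting it.
- *That events will be double counted.* The form is not among the documents. If it records onset dates, double counting can be avoided.

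**Conclusion.** The point holds in a limited form. The follow-up look-back is tied to the visit date, and this has two effects.

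The first needs no assumption about lateness. At 12 weeks, about 8% of the follow-up window lies before randomisation and duplicates days covered at baseline. This weakens the pre/post comparison unless onset dates are recorded.

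The second is conditional on late visits. At 14 weeks the scheduled form misses about the first 6 to 9 study days, and at 16 weeks about the first 20 to 23, which include the first goal weeks. Because between-visit form access is stated only for Activate, missed days could be recovered in one arm and not the other. Late visits could therefore make capture unequal even if both arms are equally late. Nothing in the documents shows that this will happen.

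The effect is confined to the adverse event comparison. The change is worth making because it replaces a stated rule at little cost.

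**What to change.** In the Data and Safety Monitoring Plan and on the form:

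1. Keep the 3-month look-back at the baseline appointment.
2. At follow-up, ask about events since the baseline appointment, with its date filled in for each participant.
3. Record an onset date for every event.
4. Count as on-study only events with onset after randomisation.
5. Report events per person-week, by period and by arm, so that unequal window lengths do not distort either comparison.

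The cost is one change of wording, one added field and a rate-based summary. The downsides are slightly longer recall when a visit is late, and pre and post windows of different length, which step 5 handles. The change closes the gap caused by visit timing; it does not by itself equalise form access between visits, which remains stated for Activate only.

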Contact between potential participants and study personnel will be initiated by the potential participants and their caregivers. Potential participants and their caregivers will respond to internet or clinic-provided advertisements and will be routed to our study website. Our study website will contain a description of study procedures and link to request contact regarding study participation. A research assistant will return contact with interested families to answer questions about the study and confirm eligibility using the screening consent script and set a date/time for consent/assent. Inclusion criteria will be the adolescents aged 13-17, and not turning 18 during study participation, with type 1 diabetes, being at least 18 months post-diagnosis, parent reported moderate to no physical activity for adolescent, ability to complete measures and intervention program in English, and access to broadband or cellular internet and currently residing in and receiving healthcare in the United States. After 30 participants are consented and enrolled into the study, we will add the following inclusion criteria: adolescent is from a marginalized racial or ethnic group. Exclusion criteria will be ward of state, active psychosis, and/or severe medical or psychiatric illness that limit participation including participation in physical activity. Participants will be provided contact information for the PI and lab to communicate during the 12-week study period about any concerns for eligibility (e.g., loss of internet, change in legal guardian status) and the PI will evaluate continued participation based on confirmation of meeting eligibility requirements.

For research involving survey, questionnaires, etc.: Describe the setting and the mode of administering the instrument and the provisions for maintaining privacy and confidentiality. Include the duration, intervals of administration, and overall length of participation.

Not applicable

Each assessment will be scheduled for a three-hour window to complete the questionnaires (80 minutes), the physical assessments (dried blood spot, abdominal circumference, blood pressure, and diabetes device reporting; 40 minutes), and at intake introduction to the treatment condition (20 minutes). Each assessment appointment is anticipated to last 2.5-3 hours.

Primary Outcomes

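### Only the Activate arm is given the adverse event form between visits, and the plan does not say whether those extra reports stay out of the planned adverse event comparisons.

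*Protocol*

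**What the plan says.** All of the adverse event collection is set out in the protocol's Data and Safety Monitoring Plan.

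- **Scheduled collection, no arm restriction:** "At baseline and 12-week follow up appointments, a research assistant will complete an adverse event form with the participant". The form asks about "any adverse events they have experienced over the past 3 months", and its stated purpose is "in order to compare adverse events pre and post study, and between study conditions".
- **Extra collection, one arm:** the next sentence says "Participants randomized to the intervention program will also have access to the adverse events form throughout the study period". The purpose given there is separate from that of the visit form: "for additional reporting should they require it".
- **General commitment:** "The research team will document and review any adverse events that occur for each participant during the study".
- **Oversight:** an independent medical monitor reviews the team's summary of adverse event reports. The plan does not say whether that summary separates visit-form reports from between-visit reports.

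Elsewhere, the protocol's screening text says: "Participants will be provided contact information for the PI and lab to communicate during the 12-week study period about any concerns for eligibility". The Treatment-as-Usual Control condition paragraph mentions tracker wear and standard care, and no between-visit adverse event form. Neither Statistical Considerations in the protocol nor the SAP contains an adverse event analysis.

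**The concern.** Two arms can be compared on adverse events only if events are looked for in the same way in each. Here both arms are asked at two visits, and one arm also holds the form for the 12 weeks between them.

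The risks that the protocol itself names for the activity program are overexertion and activity-related shifts in glucose. Mild, short-lived events of that kind could plausibly be forgotten over three months, and a form kept at hand would catch them in one arm only. Activate participants also receive weekday text support, which widens the difference in contact.

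Two readings are at stake. If extra Activate reports enter the comparison, an apparent excess could arise with no true difference. Conversely, a real excess could be dismissed as a product of easier reporting. The pre/post comparison within Activate has the same weakness: its baseline rests on recall alone, while its study period has recall plus open reporting. The section on stopping rules allows unexpected adverse events to lead to modification, hold or termination, so it matters that whoever reads the summary can tell the two sources apart.

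**Working it through.** The documents state no adverse event rate, test or power, so there is no figure of the plan's own to reproduce. The check has two parts: what the text establishes, and how large an artefact could be under stated assumptions.

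**1. The text side by side**

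| Feature | Activate | Treatment-as-usual |
|---|---|---|
| Form completed with staff at baseline and week 12 | Yes | Yes (no arm restriction stated) |
| Three-month recall at those visits | Yes | Yes |
| Form available between visits | Yes | Not described |
| Weekday text contact | Yes | Not described |
| Contact details for the investigator and lab | Yes, for eligibility concerns | Yes, for eligibility concerns |

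The study period is 12 × 7 = 84 days, so a three-month recall at week 12 covers all of it. The comparison is the stated purpose of the visit form. The between-visit form comes in the following sentence with a purpose of its own. No sentence says whether its reports are added to the comparison or kept apart.

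**2. Size if between-visit reports are pooled**

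Assumptions, none of them from the documents:
- p is the true proportion with an event, equal in both arms.
- s is the share captured by recall at week 12, equal in both arms.
- c is the share of events missed at week 12 that the between-visit form captures, in Activate only.
- Each arm has 30 participants (the protocol gives 60 in total and no allocation ratio).

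Recorded in control = p·s. Recorded in Activate = p·[s + (1 − s)·c]. The apparent ratio is therefore 1 + c·(1 − s)/s, and p cancels.

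| s | c = 0 | c = 0.25 | c = 0.50 | c = 0.75 |
|---|---|---|---|---|
| 0.95 | 1.00 | 1.01 | 1.03 | 1.04 |
| 0.80 | 1.00 | 1.06 | 1.13 | 1.19 |
| 0.60 | 1.00 | 1.17 | 1.33 | 1.50 |

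The 1.50 corner means that total capture is 0.90 in Activate against 0.60 in control (0.90/0.60). It requires an optional, self-initiated form to catch (0.90 − 0.60)/(1 − 0.60) = 75% of what the visit missed.

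In participants, the excess in Activate is 30·p·(1 − s)·c:
- Smallest, at p = 0.2, s = 0.95, c = 0.25: 30 × 0.2 × 0.05 × 0.25 = 0.075, about 0.1.
- At p = 0.6, s = 0.60, c = 0.50: 30 × 0.6 × 0.40 × 0.50 = 3.6.

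**3. Size if only visit forms are compared**

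The pooling term disappears and the ratio becomes s(Activate)/s(control). With equal recall it is 1.00. If having filed a form makes events easier to recall at week 12, it is above 1. For example, recall of 0.90 against 0.80 gives 0.90/0.80 = 1.13. Restricting the comparison to visit forms removes the first route but not this second one. Giving both arms the same form addresses the form's own part in the second.

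**The case against.** The strongest reply is that the plan, read plainly, already compares like with like. The comparison is the purpose of the visit form, which both arms complete with a recall window that spans the study. The Activate-only form has a separate purpose, additional reporting, and extra watchfulness over the arm exposed to the activity program is an understandable safety measure in a small, minimal-risk trial. Adverse events are not among the listed outcomes, no test is planned for them, and no stopping threshold uses a between-arm rate. Any artefact would overstate harm rather than conceal it.

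Much of this stands, and it rules out three stronger readings that a reader might infer:

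- **That the comparison is biased as planned.** Bias needs a further step, either pooling or better recall in Activate. The plan states neither.
- **That controls have no way to report an event between visits.** The team undertakes to document events for every participant, and all families have contact details, though these are given for eligibility concerns. What is missing is a described form, not demonstrably every route.
- **That the monitor sees all reports merged.** The protocol mentions a summary of reports. It does not say that the sources are merged, nor that they are separated.

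The reply does not remove the stated difference between arms in how events can be reported, and it does not supply the missing rule on which reports count. That any artefact would exaggerate harm is limited comfort, because the known asymmetry also gives a reason to discount a true excess.

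**Conclusion.** The point holds in a limited form. Between-visit ascertainment of adverse events differs by arm by design, a between-arm and a pre/post comparison are planned, and nothing states that the extra Activate reports are left out of those comparisons or shown separately to the medical monitor. If they are pooled, or if filing them improves week-12 recall, the artefact runs toward more recorded events on Activate.

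Its size cannot be obtained from the documents. Under assumed capture rates the apparent ratio lies between 1.0 and about 1.5, and the upper end depends on poor recall together with heavy use of an optional form. With visit forms only and equal recall it is 1.00. It would be wrong to conclude that a true null will look like harm: that follows only under the conditions named here. This is an inexpensive improvement to safety ascertainment and does not touch the efficacy analysis.

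**What to change.** Three changes, best made together:

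1. Give treatment-as-usual participants the same between-visit adverse event form, with the same instructions, for the full 12 weeks.
2. State in the Data and Safety Monitoring Plan, and in the SAP if adverse events are to be reported there, that the between-arm and pre/post comparisons use only the forms completed at the baseline and 12-week visits.
3. List between-visit reports separately by arm, and keep that separation in the summary sent to the medical monitor.

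In the model above, equal access with equal use, or restriction to visit forms with equal recall, brings the ratio to 1.00. Doing both guards against unequal use of the form and against its effect on recall. The weekday texts remain a difference because they are part of the intervention, and that should be acknowledged when the events are interpreted.

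The cost is one form link in the control-arm instructions, a few sentences of text and a few more reports to review. No treatment procedure changes.
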